6.4 TOXICITY CRITERIA

The following adverse event management guidelines are intended to ensure the safety of each patient while on the study. The descriptions and grading scales found in the revised NCI Common Terminology Criteria for Adverse Events (CTCAE) version 4.0 will be utilized for AE reporting. All appropriate treatment areas should have access to a copy of the CTCAE version 4.0. A copy of the CTCAE version 4.0 can be downloaded from the CTEP web site (http://ctep.cancer.gov/protocolDevelopment/electronic_applications/ctc.htm#ctc_40).

7 NIH REPORTING REQUIREMENTS/DATA AND SAFETY MONITORING PLAN

7.1 DEFINITIONS

Please refer to definitions provided in Policy 801: Reporting Research Events found [here](#).

7.2 OHSRP OFFICE OF COMPLIANCE AND TRAINING/IRB REPORTING

7.2.1 Expedited Reporting

Please refer to the reporting requirements in Policy 801: Reporting Research Events and Policy 802 Non-Compliance Human Subjects Research found [here](#). Only IND Safety Reports that meet the definition of an unanticipated problem will need to be reported per these policies.

7.2.2 IRB Requirements for PI Reporting at Continuing Review

Please refer to the reporting requirements in Policy 801: Reporting Research Events found [here](#).

7.3 NCI CLINICAL DIRECTOR REPORTING

Problems expeditiously reported to the OHSRP in iRIS will also be reported to the NCI Clinical Director. A separate submission is not necessary as reports in iRIS will be available to the Clinical Director.

In addition to those reports, all deaths that occur within 30 days after receiving a research intervention should be reported via email to the Clinical Director unless they are due to progressive disease.

To report these deaths, please send an email describing the circumstances of the death to [name] at [contact] within one business day of learning of the death.

7.4 NIH REQUIRED DATA AND SAFETY MONITORING PLAN

7.4.1 Principal Investigator/Research Team

The clinical research team will meet on a regular basis when patients are being actively treated on the trial to discuss each patient. Decisions about dose level enrollment and dose escalation if applicable will be made based on the toxicity data from prior patients.

All data will be collected in a timely manner and reviewed by the principal investigator or a lead associate investigator. Events meeting requirements for expedited reporting as described in section **7.2.1** will be submitted within the appropriate timelines.

The principal investigator will review adverse event and response data on each patient to ensure safety and data accuracy. The principal investigator will personally conduct or supervise the investigation and provide appropriate delegation of responsibilities to other members of the research staff.

8 SPONSOR SAFETY REPORTING

8.1 DEFINITIONS

8.1.1 Adverse Event

Any untoward medical occurrence in a patient or clinical investigation subject administered a pharmaceutical product and which does not necessarily have a causal relationship with this treatment. An adverse event (AE) can therefore be any unfavorable and unintended sign (including an abnormal laboratory finding), symptom, or disease temporally associated with the use of a medicinal (investigational) product, whether or not related to the medicinal (investigational) product (ICH E6 (R2))

8.1.2 Serious Adverse Event (SAE)

An adverse event or suspected adverse reaction is considered serious if in the view of the investigator or the sponsor, it results in any of the following:

- Death,
- A life-threatening adverse event (see section **8.1.3**)
- Inpatient hospitalization or prolongation of existing hospitalization
 - A hospitalization/admission that is pre-planned (i.e., elective or scheduled surgery arranged prior to the start of the study), a planned hospitalization for pre-existing condition, or a procedure required by the protocol, without a serious deterioration in health, is not considered a serious adverse event.
 - A hospitalization/admission that is solely driven by non-medical reasons (e.g., hospitalization for patient convenience) is not considered a serious adverse event.
 - Emergency room visits or stays in observation units that do not result in admission to the hospital would not be considered a serious adverse event. The reason for seeking medical care should be evaluated for meeting one of the other serious criteria.
- Persistent or significant incapacity or substantial disruption of the ability to conduct normal life functions
- A congenital anomaly/birth defect.
- Important medical events that may not result in death, be life-threatening, or require hospitalization may be considered a serious adverse drug experience when, based upon appropriate medical judgment, they may jeopardize the patient or subject and may require medical or surgical intervention to prevent one of the outcomes listed in this definition.

8.1.3 Life-threatening

An adverse event or suspected adverse reaction is considered "life-threatening" if, in the view of either the investigator or sponsor, its occurrence places the patient or subject at immediate risk of death. It does not include an adverse event or suspected adverse reaction that, had it occurred in a more severe form, might have caused death. (21CFR312.32)

8.1.4 Severity

The severity of each Adverse Event will be assessed utilizing the CTCAE version 4.0.

8.1.5 Relationship to Study Product

All AEs will have their relationship to study product assessed using the terms: related or not related.

- Related – There is a reasonable possibility that the study product caused the adverse event. Reasonable possibility means that there is evidence to suggest a causal relationship between the study product and the adverse event.
- Not Related – There is not a reasonable possibility that the administration of the study product caused the event.

8.2 ASSESSMENT OF SAFETY EVENTS

AE information collected will include event description, date of onset, assessment of severity and relationship to study product and alternate etiology (if not related to study product), date of resolution of the event, seriousness and outcome. The assessment of severity and relationship to the study product will be done only by those with the training and authority to make a diagnosis and listed on the Form FDA 1572 as the site principal investigator or sub-investigator. AEs occurring during the collection and reporting period will be documented appropriately regardless of relationship. AEs will be followed through resolution.

SAEs will be:

- Assessed for severity and relationship to study product and alternate etiology (if not related to study product) by a licensed study physician listed on the Form FDA 1572 as the site principal investigator or sub-investigator.
- Recorded on the appropriate SAE report form, the medical record and captured in the clinical database.
- Followed through resolution by a licensed study physician listed on the Form FDA 1572 as the site principal investigator or sub-investigator.

For timeframe of recording adverse events, please refer to section 6.1. All serious adverse events recorded from the time of first investigational product administration must be reported to the sponsor.

8.3 REPORTING OF SERIOUS ADVERSE EVENTS

Any AE that meets protocol-defined serious criteria or meets the definition of Adverse Event of Special Interest that require expedited reporting must be submitted immediately (within 24 hours of awareness) to OSRO Safety using the CCR SAE report form.

All SAE reporting must include the elements described in section 8.2.

SAE reports will be submitted to the Center for Cancer Research (CCR) at: [contact] and to the CCR PI and study coordinator. CCR SAE report form and instructions can be found at:

<https://ccrod.cancer.gov/confluence/pages/viewpage.action?pageId=157942842>

Following the assessment of the SAE by OSRO, other supporting documentation of the event may be requested by the OSRO Safety and should be provided as soon as possible.

8.5 REPORTING PREGNANCY

8.5.1 Maternal exposure

If a patient becomes pregnant during the course of the study, the study treatment should be discontinued immediately, and the pregnancy reported to the Sponsor no later than 24 hours of when the Investigator becomes aware of it. The Investigator should notify the Sponsor no later than 24 hours of when the outcome of the Pregnancy become known,

Pregnancy itself is not regarded as an SAE. However, congenital abnormalities or birth defects and spontaneous miscarriages that meet serious criteria (section **8.1.2**) should be reported as SAEs.

The outcome of all pregnancies (spontaneous miscarriage, elective termination, ectopic pregnancy, normal birth, or congenital abnormality) should be followed up and documented.

8.5.2 Paternal exposure

Male patients should refrain from fathering a child or donating sperm during the study and for 30 days after the last dose of Zotiraciclib (TG02)

Pregnancy of the patient's partner is not considered to be an AE. However, the outcome of all pregnancies (spontaneous miscarriage, elective termination, ectopic pregnancy, normal birth, or congenital abnormality) occurring from the date of the first dose until 30 days after the last dose should, if possible, be followed up and documented.

8.6 REGULATORY REPORTING FOR STUDIES CONDUCTED UNDER CCR-SPONSORED IND

Following notification from the investigator, CCR, the IND sponsor, will report any suspected adverse reaction that is both serious and unexpected. CCR will report an AE as a suspected adverse reaction only if there is evidence to suggest a causal relationship between the study product and the adverse event. CCR will notify FDA and all participating investigators (i.e., all investigators to whom the sponsor is providing drug under its INDs or under any investigator's IND) in an IND safety report of potential serious risks from clinical trials or any other source, as soon as possible, in accordance to 21 CFR Part 312.32.

All serious events will be reported to the FDA at least annually in a summary format.

9 CLINICAL MONITORING PLAN

As a sponsor for clinical trials, FDA regulations require the CCR to maintain a monitoring program. The CCR's program allows for confirmation of: study data, specifically data that could

affect the interpretation of primary and secondary study endpoints; adherence to the protocol, regulations, ICH E6, and SOPs; and human subjects protection. This is done through independent verification of study data with source documentation focusing on:

- Informed consent process
- Eligibility confirmation
- Drug administration and accountability
- Adverse events monitoring
- Response assessment.

The monitoring program also extends to multi-site research when the CCR is the coordinating center.

This trial will be monitored by personnel employed by a CCR contractor. Monitors are qualified by training and experience to monitor the progress of clinical trials. Personnel monitoring this study will not be affiliated in any way with the trial conduct.

De-escalate if # of patients who experienced DLT >=	2	3	4	6	7	8
Eliminate if # of patients who experienced DLTs >=	3	5	6	7	9	10

When using Table 13, please note the following:

- (a) “Eliminate” means that we eliminate the current and higher doses from the trial to prevent treating any future patients at these doses because they are overly toxic.
- (b) When we eliminate a dose, we automatically de-escalate the dose to the next lower level. When the lowest dose is eliminated, we stop the trial for safety. In this case, no dose should be selected as the MTD.
- (c) If none of the actions (i.e., escalation, de-escalation or elimination) is triggered, we treat the new patients at the current dose.
- (d) If the current dose is the lowest dose and the rule indicates dose de-escalation, we will treat the new patients at the lowest dose unless the number of DLTs reaches the elimination boundary, at which point we will terminate the trial for safety.
- (e) If the current dose is the highest dose and the rule indicates dose escalation, we will treat the new patients at the highest dose.
- (f) If the number of patients treated at the current (or any) dose reaches 12, we will stop the trial early and select the MTD as described below.

3. Repeat step 2 until the maximum sample size of 24 is reached or the trial is stopped.

After the trial is completed, we select the MTD based on isotonic regression as specified previously. [46] Specifically, we select as the MTD the dose for which the isotonic estimate of the toxicity rate is closest to the target toxicity rate. If there are ties, we select the higher dose level when the isotonic estimate is lower than the target toxicity rate; and we select the lower dose level when the isotonic estimate is greater than the target toxicity rate.

After identifying the MTD for each of the TMZ dosing schedules in combination with Zotiraciclib (TG02) (i.e., 125mg/m² TMZ on days 1-7 and 15-21 per cycle, and 50 mg/m² TMZ daily), cohort expansion will be conducted independently at each of the MTDs until the total number of patients treated at each of the MTDs reaches 18 patients (including the patients who have been treated in the dose-finding part). The dosing schedule with a higher PFS4 at 4 months (PFS4) will be selected and used in phase II. If the difference between the PFS4 values from the two full cohorts treated at each of the MTDs is less than 10% of the average of the two PFS4 values, then the dosing schedule with fewer AEs will be selected as the “winner.” During the cohort expansion phase, the elimination rule displayed in the last row of Table 13 will be used to monitor toxicity. Given the cohort expansion of 18 patients at the MTD, there is 72.6% chance to correctly pick the better schedule when the PFS4 for two schedules are 50% and 60% (i.e., 10% difference in PFS4), respectively; and there is 81.9% chance to correctly pick the better schedule when the PFS4 for two schedules are 50% and 65% (i.e., 15% difference in PFS4)

Table 14 shows the operating characteristics of the BOIN design for this trial with 4 scenarios defined by different DLT rates for 4 doses. These operating characteristics are based on 1,000 simulations of the trial using R package “BOIN”, which is available from CRAN. The operating characteristics show that the design selects the true MTD with high probabilities and allocates more patients to the dose levels with the DLT rate closest to the target of 0.35.

Table 14 Operating Characteristics of the BOIN design

	Dose level				Number of pts	% early stopping
	-1	0	1	2		
True DLT rate	0.05	0.15	0.35	0.47		
Selection %	0.3	25.3	54.3	20.1	19.7	0.0
# pts treated	0.4	7.5	8.5	3.4		
True DLT rate	0.12	0.35	0.44	0.55		
Selection %	16.2	59.3	21.2	3.3	18.5	0.0
# pts treated	4.0	9.7	3.9	1.0		
True DLT rate	0.35	0.50	0.55	0.62		
Selection %	57.0	28.3	4.3	0.2	17.1	10.2
# pts treated	8.2	7.4	1.4	0.1		
True DLT rate	0.05	0.10	0.16	0.35		
Selection %	0.1	4.4	24.2	71.3	20.7	0.0
# pts treated	0.2	4.6	7.2	8.7		

In phase I, for each arm, the maximum sample size of 24 patients will be used for dose finding. As there are 4 doses, on average at least 6 patients will be treated at the MTD. After the MTD is selected, cohort expansion will be conducted at the MTD until the total number of patients treated at the MTD reaches 18 patients (including the patients who have been treated in the dose-finding part). Thus, no more than 12 additional patients will be enrolled during the cohort expansion phase. Therefore, the maximum number of patients for phase I, including dose finding and cohort expansion, is 24+12=36 patients per treatment arm, and 72 in total for two treatment arms.

During the interim analysis of the Phase I study, we identified TG02 of 250 mg as the MTD in both Arm 1 and Arm 2. Cohort expansion was conducted independently at each of the MTD into treatment arms, and the PSF4 was found to be 38% in Arm 1 and 25% in Arm 2. Therefore, based on the preplanned analysis, the DD TMZ dosing schedule is considered a “winner” to be used in Phase II study. However, a better PFS was found in patients who received TG02 at dose level 0, compared to those received TG02 at dose level 1, which is MTD, in Arm 1, the winner arm, suggesting the lower dose with the scheduled TMZ may be sufficient if not more beneficial for patients with recurrent high grade astrocytoma. However, we cannot make the conclusion based on the small sample number in Arm 1 at dose level 0. Therefore, we would like to continue enrolling to the maximum, allow the additional 12 patients enrolled to be treated with TG02 at dose level 0 combined with dd TMZ.

We do not plan to change the study design. The primary endpoint is still toxicity. The objective is to add a small cohort expansion to better characterize the dose-toxicity relationship and obtain some preliminary efficacy readout to determine RP2D. If PFS4 month difference between MTD and (MTD-1) is less than 5%, select the lower dose, I.e., MTD-1, as the RP2D; otherwise select the MTD as RP2D.

There should not be safety concerns because additional patients will be treated with TG02 at a dose that is lower than the MTD that was identified previously.

The purpose for enrolling more patients is to further define a dosage not only safe but optimal for the patients before we move to Phase II study. Only AE and PFS4 will be recorded in these subjects.

10.2 PHASE II COMPONENT:

A randomized phase II trial will be used to compare the combination of Zotiraciclib (TG02) plus TMZ (selected from phase I) with TMZ alone in patients with recurrent grade III or IV malignant glioma. The TMZ alone arm will use the same dosing schedule as it is in the combination arm. The primary endpoint is progression free survival. We will enroll at least 10 patients and at most 40 patients for each arm at a rate of 4 patients per month. Patients will be equally randomized into two arms. Patients' KPS, MGMT promoter methylation status of the tumors and the presence of measurable disease at study entry will be used as stratification factors. We will follow all patients for at least 12 months, and monitor futility and toxicity as described below. We will use the methods described by Thall et al., to monitor progression-free survival (PFS), and we will stop enrolling patients early if, based on the available data, we have reason to believe that the median PFS of the Zotiraciclib (TG02) plus TMZ arm is less than that of the TMZ arm.^[50] Formally, we will stop enrolling patients early if

$$\Pr(\text{median PFS}_{\text{TG02+TMZ}} \geq \text{median PFS}_{\text{TMZ}} \mid \text{data from the trial}) < 0.78,$$

The futility monitoring will be conducted after enrolling 20, 40 and 60 patients (for two arms combined). Below are the operating characteristics of the above futility monitoring rule, assuming that the median PFS of the TMZ alone arm is 3 months.

Table 15 Operating Characteristics of the Futility Monitoring rule

	Median PFS for Zotiraciclib (TG02) +TMZ (months)				
	1	2	3	4	5
Early stop probability	0.999	0.812	0.374	0.170	0.097
Average sample size	23.7	42.1	62.6	70.9	74.7

Similar Bayesian methods will also be used to monitor the rate of DLT. We will monitor the two arms independently. Specifically, we will stop enrolling patients if the $\Pr(\text{DLT} > 35\% \mid \text{data}) > 0.9$. That is, we will stop enrolling patients if the data indicate that there is more than 90% chance that the true DLT rate is higher than 35%. This decision rule gives the following stopping rule, assuming a Beta (0.1, 0.4) prior distribution for DLT rate,

Stop enrolling pts if $[\# \text{ of pts with DLT}] / [\# \text{ of pts evaluated}] \geq 4/5, 6/10, 10/20, \text{ and } 15/30$.

Below are the operating characteristics of the toxicity monitoring rule.

Table 16: Operating Characteristics of the Toxicity Monitoring Rule

	True toxicity rate				
	0.2	0.3	0.4	0.5	0.6

Early stop probability	0.014	0.096	0.345	0.716	0.939
Average sample size	39.6	37.3	31.0	21.3	13.5

At progression, patients on the control arm will be offered treatment with Zotiraciclib (TG02) in combination with continued treatment with TMZ. If an effective salvage regimen, this may impact the secondary OS endpoint, but will not affect the primary endpoint of the study. The maximum number is 80 patients.

Statistical Analysis Plan

We will use descriptive statistics to summarize the demographic and clinical characteristics of patients. We will tabulate adverse events by grade by dose level and overall. For the cohort expansion and phase II component, we will estimate the proportion of patients with response with 95% exact binomial confidence intervals, and use descriptive statistics to summarize response duration. We will estimate PFS/OS with the Kaplan-Meier product limit estimator. Log-rank test will be used to compare the PFS/OS between Zotiraciclib (TG02)+TMZ and TMZ.

Changes of symptom burden (i.e., MDASI-BT) through study time points will be assessed by paired t-tests and linear mixed model. In the mixed model, subject-specific random intercept will be used to account for within-subject correlation, and measurement time will be included as a covariate. A sample size of 40 patients has 80% power to detect an effect size of 0.454 between time points using a two-tailed test with an alpha of 0.05. The two-sample t-test and linear mixed model will be used to evaluate differences in symptom burden using the MDASI-BT between Zotiraciclib (TG02) plus TMZ and TMZ. Cox proportional hazard model will be used to evaluate the relationship between MDASI-BT and disease progression. Logistic regression will be used to evaluate the relationship between MDASI-BT and tolerance to treatment.

Treatment effects will be evaluated by advanced MRI imaging study. Perfusion and diffusion – based MRI parameters, including but not restricted to blood volume, blood flow mean and median Apparent Diffusion Coefficient (ADC) value will be analysed. Results will be summarized. The mean and median value at different time points will be tabulated. Changes in such parameters will be analysed for statistical significance and correlate with the disease status.

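### The 72.6% and 81.9% chances of picking the better TMZ schedule do not describe the written selection rule, which sends about a fifth of outcomes to AE counts

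*Combined protocol and SAP*

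**What the plan says.** Section 10.1 expands each arm at its MTD "until the total number of patients treated at each of the MTDs reaches 18 patients", counting patients already treated at that dose during dose finding. The main selection rule is "The dosing schedule with a higher PFS4 at 4 months (PFS4) will be selected and used in phase II". A second step covers near-ties. If the difference between the two PFS4 values "is less than 10% of the average of the two PFS4 values", "then the dosing schedule with fewer AEs will be selected as the “winner". The zone is relative to the observed average and is not a fixed number of percentage points.

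The same paragraph then gives the operating characteristics of the choice: "there is 72.6% chance to correctly pick the better schedule when the PFS4 for two schedules are 50% and 60" per cent, and "there is 81.9% chance to correctly pick the better schedule when the PFS4 for two schedules are 50% and 65" per cent. It does not say how these were obtained, does not mention the near-tie step in connection with them, and assumes nothing about AE counts on either schedule. Sections 3.1.1 and 3.2.1.2 give only the higher-PFS4 rule, without the near-tie step.

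Later in Section 10.1 the interim result is reported: "the PSF4 was found to be 38% in Arm 1 and 25% in Arm 2". On that basis dd TMZ is named as the schedule for Phase II.

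**The concern.** A probability of correct selection belongs to a particular decision rule. The written rule has two steps, and the second depends on AE counts. Its chance of success cannot be calculated without saying how likely the better schedule is to have fewer AEs. Because no such assumption is stated, 72.6% and 81.9% cannot be derived from the rule beside them.

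These are the only design-stage figures for schedule selection; Table 14 concerns MTD selection. A reader quoting them would be quoting a success rate that the written rule need not have. The gap could be appreciable in either direction if AE burden and efficacy go together, because the AE step can overrule a PFS4 difference that already points to the better schedule.

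**Working it through.** **Inputs, all from Section 10.1.** 18 patients per schedule; true PFS4 of 50% vs 60% and of 50% vs 65%; a near-tie zone of less than 10% of the average observed PFS4; fewer AEs wins inside the zone. Assumed here: all 18 per schedule are evaluable at 4 months, PFS4 is a yes/no outcome without censoring, and the two schedules are independent.

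**Set-up.** Let X ~ Binomial(18, 0.50) be the number progression-free at 4 months on the worse schedule, and Y ~ Binomial(18, 0.60) or Binomial(18, 0.65) the number on the better one. All 19 × 19 pairs (X, Y) are enumerated exactly.

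**Step 1: reproduce the printed figures.** Take the rule that the higher PFS4 wins and exact ties are split evenly. P(correct) = P(Y > X) + ½ P(Y = X).

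- 50% vs 60%: 0.6706 + ½ × 0.1106 = 0.7259 (printed: 72.6%).
- 50% vs 65%: 0.7744 + ½ × 0.0879 = 0.8184 (printed: 81.9%).

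The first agrees to the printed digit and the second to within 0.1 point. A normal approximation gives 72.8% and 82.2%, a poorer match.

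**Step 2: which outcomes go to AE counts under the written rule.** In counts, the condition is |Y − X|/18 < 0.10 × (X + Y)/36, that is |Y − X| < 0.05 × (X + Y). Exact ties qualify. A gap of one patient qualifies when X + Y > 20, so from 10 vs 11 upward. A gap of two would need X + Y > 40, which is impossible because the maximum is 36.

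| | 50% vs 60% | 50% vs 65% |
|---|---|---|
| Better schedule chosen on PFS4 | 60.8% | 70.5% |
| Worse schedule chosen on PFS4 | 17.7% | 10.0% |
| Decided by AE counts | 21.4% | 19.5% |
| – of which exact ties | 11.1% | 8.8% |
| – of which one-patient gaps | 10.3% | 10.7% |

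The first column adds to 99.9% through rounding; unrounded it is 0.6085 + 0.1775 + 0.2141 = 1.000.

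**Step 3: overall chance of a correct pick.** P(correct) = P(correct on PFS4) + q × P(decided by AEs), where q is the chance that the AE step favours the better schedule.

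| q | 50% vs 60% | 50% vs 65% |
|---|---|---|
| 0 (AEs always favour the worse schedule) | 60.8% | 70.5% |
| ½ (AEs unrelated to efficacy) | 0.6085 + ½ × 0.2141 = 71.6% | 0.7049 + ½ × 0.1949 = 80.2% |
| 1 (AEs always favour the better schedule) | 82.3% | 90.0% |

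**Step 4: why the neutral figures are lower.** Within the zone, one-patient gaps favour the better schedule more often than the worse one (0.0621 vs 0.0414; 0.0696 vs 0.0375). Replacing them by a coin flip loses half the difference: ½ × 0.0207 = 1.0 point and ½ × 0.0321 = 1.6 points from the Step 1 values. Against the printed figures the shortfalls are 72.6 − 71.6 = 1.0 and 81.9 − 80.2 = 1.7 points.

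**Step 5: was the AE step used?** The interim values of 38% and 25% average 31.5%, so the zone covers gaps below 3.15 points. The observed gap is 13 points, or 13/31.5 = 41% of the average. The AE step was not triggered.

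**The case against.** The best defence is that the figures barely move under a neutral AE step: by 1.0 and 1.7 points. That stands, and it limits the importance of the point.

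It can also be said that the simpler rule is only inferred. The plan states no method, and the match for the second figure is off by 0.1 point. Had the figures come from 1,000 simulated trials (an assumption; Section 10.1 mentions that number only for Table 14), the standard errors would be √(0.716 × 0.284/1000) = 1.4 points and √(0.802 × 0.198/1000) = 1.3 points. The printed values would then lie about 0.7 and 1.3 standard errors from the written rule with neutral AEs. So the origin of the figures remains an inference. But even on that account the plan would have needed an AE assumption that it does not state.

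Three stronger readings are tempting, and the documents support none of them. A reader might infer that the printed figures are optimistic, because the chance falls to 60.8% or 70.5% if the better schedule has more AEs. The opposite case gives 82.3% or 90.0%, and the plan does not say which schedule would have more AEs at the MTD. A reader might infer that these figures are all that supports taking dd TMZ forward. Section 10.1 bases that choice on observed PFS4. And a reader might infer that the choice itself is in doubt. It was made well outside the near-tie zone.

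Finally, Section 10.2 estimates PFS by Kaplan-Meier. With censoring, exact ties and one-patient gaps would occur with different frequency, so the decimals above hold only for complete binary data.

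**Conclusion.** The point holds as a mismatch between a stated rule and its stated operating characteristics. The printed 72.6% and 81.9% closely match a rule without the near-tie step, while the written rule leaves 21.4% and 19.5% of outcomes to AE counts, about half of them one-patient differences and not ties. The chance of a correct pick under the written rule is a range: 60.8% to 82.3% at 50% vs 60%, and 70.5% to 90.0% at 50% vs 65%. The neutral values are 71.6% and 80.2%. All of this rests on 18 evaluable patients per schedule and uncensored binary PFS4. The documents do not show that the printed figures are biased upward overall, and the selection of dd TMZ is unaffected. This is a minor reporting correction.

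**What to change.** In Section 10.1, replace 72.6% and 81.9% with the figures for the written rule and state the assumption behind them. For example: with 18 evaluable patients per schedule, PFS4 treated as binary without censoring, and AE counts unrelated to efficacy, the chance of selecting the better schedule is 71.6% for true PFS4 of 50% vs 60% and 80.2% for 50% vs 65%; AE counts decide 21.4% and 19.5% of outcomes, and the chance ranges from 60.8% to 82.3% and from 70.5% to 90.0% according to whether AEs favour the worse or the better schedule.

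The cost is one sentence and slightly less favourable figures. The design, the sample size and the chosen schedule stay as they are.
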